# Economic evaluation

- EQ-5D-5L (EuroQol Group, 2009). The EQ-5D-5L measures the quality of life by means of five dimensions, including mobility, self-care, usual activities, pain/discomfort, and anxiety/depression. In addition it contains a visual analogue scale to determine Quality Adjusted Life Years (QALYs). The EQ-5D-5L shows to be a valid instrument (Janssen et al., 2013).
- Trimbos/iMTA questionnaire for costs associated with psychiatric illness (Tic-P; Hakkaart, Van Straten, Donker, & Tiemens, 2002). The TiC-P is a 38-item, self-report inventory measuring resource use, such as use of care, medication and illness related to work. It measures both direct costs, i.e. care consumption of people suffering from psychiatric illness, and indirect costs, i.e. costs associated with production loss. The TiC-P shows good reliability (Bouwmans et al., 2013).

## Cognitive measures

- *Stroop Task* (Stroop, 1935). Subjects are instructed to name the colour of the printed text on the card, not the colour of the word that is written. This tasks measures interference in attention.
- *Emotional Stroop Task* (Williams et al., 1996). This is an adapted version of the original colour Stroop task. Cards are filled with neutral stimuli (XXXX), negative words (e.g. 'sadness') and positive words (e.g. 'happy'), reaction time per card is measured.
- *Breathing Focus Task* (Hayes, Hirsch, Krebs, & Matthews, 2010). This task measures state rumination. Subjects are instructed to concentrate on their breathing for 5 minutes. The computer signals at random points in time, on which the subjects are instructed to tell the research assistant whether they focused on breathing or not. Furthermore, they are asked to tell whether their thoughts were positive, negative or neutral at the moment of the signal. After this, the subjective experience of the breathing task is assessed shortly (Hayes et al., 2010).
- Self Referent Encoding Task (Joormann et al., 2006). This task measures memory bias for emotional information. 24 words are presented on a computer screen (12 negative, 12 positive). Subjects are asked to rate whether or not the word describes them. After this, subjects are distracted for 3 minutes with a trail making task. The trail making task is followed by a free recall phase, in which they have to 3 minutes to write down as much words as they remember.
- Pavlovian to instrumental transfer task (Geurts et al., 2013; Huys et al., 2011). This task
  assesses positive and negative affecte bias on goal-oriented, instrumental behaviour. At
  first, subjects are trained to react to instrumental stimuli with which they can earn small
  amounts of money (5 cents). Next, we show subjects neutral pictures that we then
  associate with monetary wins and losses. By this latter classical (or Pavlovian) conditioning
  procedure these neutral pictures acquire an affective valence and become conditioned
  stimuli (CS) with appetitive and aversive valence respectively. Finally we ask subjects to
  react to the instrumental stimuli again, but now also show them the CS on the background.
  The CS-dependent change in instrumental behaviour then is a measure of Pavlovian
  affective bias.

# 6.1.3 Other study parameters

# Baseline parameters

- Age
- Gender
- Ethnicity
- Level of education
- Marital status
- Employment status
- BD type (bipolar I or II)
- Age at onset
- Time since last episode of depression or (hypo)mania
- Number of previous episodes (manic and depressed, reported separately)
- Types and dose of medication being used
- Previous treatment with CBT and/or IP(SR)T (yes/no)
- Suicide attempt (lifetime; yes/no)
- Number of previous hospitalizations due to either manic or depressive episode
- Comorbid psychiatric diagnoses

## Measures for adherence

Adherence to mindfulness practice and medication use will be assessed using prospective daily registration on the Life Chart.

## 6.2 Randomisation, blinding and treatment allocation

Randomisation will be performed within the datamanagement system Castor EDC. This will consist of stratified, variable block randomisation with the following stratification variables: Location (site); Gender; Depression (current versus remitted); BD type (I versus II); and number of previous episodes (<12 versus =/> 12). This system also allows for blinded (concealed) allocation such that research assistants on site can be kept blind to condition. MBCT teachers on site will be notified of the allocation to MBCT, allowing them to invite the patient to participate and coordinate further arrangements. As only assessors will be blind to treatment allocation due to the nature of the intervention, no indications for breaking the randomization code are pre-specified. In case of adverse reactions, patients are encouraged to discuss this with their MBCT teacher and responsible clinician.

## 6.3 Study procedures

Figure 2 provides a flowchart of the study procedures from referral to the final assessment. Patients will be recruited from several specialized, outpatient clinics in the Netherlands; ProPersona, Dimence, and Altrecht, and through the patient association; Vereniging voor Manisch Depressieven en Betrokkenen (VMDB). They will receive a letter from their attending clinicans, informing them about the study with an included information leaflet. This way, patients are free to choose whether to participate in the study, without feeling obligated to their clinicans when asked face-to-face. Interested patients are, after verbal consent is obtained, invited for a screening by telephone to assess global eligibility. Eligible patients will receive more information and a detailed description of the study procedure. After one week, patients will be contacted by telephone to assess whether they are still interested in participation. Patients who are still interested to participate will be invited for intake with a research assistant, where informed consent is obtained. They are thoroughly screened for in- and exclusion criteria with use of the SCID-I and YMRS. Altogether, this will take about 1.5 hours. When patients are still eligible and interested, they are invited for baseline assessment (T0), which consists of several clinician administered measures (IDS-C and FAST), which will take about 20 minutes. After a short pause, participants are asked to conduct five short computer tasks (Stroop, Emotional Stroop Task, Breathing Focus Task, Self Referent Encoding Task, and Attentional Control Scale). This will take about onee hour. However, it is possible for participants to do only the first part of these measures, so they can skip the computer tasks if necessary. Furthermore, participants are asked to fill in several self-report questionnaires at home (STAI, brooding subcale of RRS, CHIME, SCS-SF, MHC-SF, RPA, CTQ, TiC-P, and EQ-5D-5L). After baseline assessment, patients are randomised to one of two groups: TAU or MBCT + TAU. Participants in the intervention group (MBCT + TAU) will receive an eight-week MBCT training, during which they daily have to document mood fluctuations, changes in medication, and major life events in the Life Chart. Furthermore, participants are asked to document adherence and adverse events in a personal diary. Participants in the comparator group (TAU) will receive their treatment as usual, while they daily document in the Life Chart as well. After three months (T1), participants are invited for follow-up assessment, during which the clinician administered questionnaires (YMRS, IDS-C, FAST, SCID-I) and computer tasks will be conducted again. Furthermore, patients are asked to fill out the online self-report questionnaires a second time. More follow-up assessments will take place after 6 months (T2), 9 months (T3), 12 months (T4), and 15 months (T5). During T2, T3, and T4 assessments patients are approached by telephone to assess depressive, manic, and anxiety symptoms, and global functioning over the past three months (IDS-C, YMRS, FAST, and SCID-I to assess manic and depressive symptoms retrospectively). Furthermore, during these assessments patients are asked to fill out the online questionnaires as well. The assessment at 15 months follow-up (T5), will consist of the clinician adminstered meassurements (IDS-C, YMRS, FAST) and the online self-report measurements (STAI, brooding subcale of RRS, CHIME, SCS-SF, MHC-SF, RPA, TiC-P, EQ-5D-5L). Table 1 provides an overview of the assessments. After 15 months of follow-up the study will end, after which participants in the comparator group will be given the opportunity to participate in a MBCT-course as well.

Recruitment via mental health professionals' referrals or self-referrals.							
Interested individuals screened by telephone to assess global eligibility after verbal consent is obtained.							
Does patient (probably) meet inclusion (and not exclusion criteria?							
Yes							
Study procedure explained in detail and study information is provided. Patients get one week (or longer if needed) to decide whether or not to participate.							
Patient still interested in participation? No → Exclude							
Yes							
Patient is invited for the research interview, in which the in- and exclusion criteria are assessed in detail. Informed consent is collected.							
└─────────────────────────────────────							
Eligible and informed consent obtained?							
Yes							
Randomization (stratification variables: research centre; gender; depression status (current versus remitted); type of Bipolar Disorder; number of previous episodes (<12 versus =/> 12).							
T0 assessment (baseline)							
( TAU + MBCT ) ( TAU )							
-MBCT intervention (8 weeks)							
T1 assessment (3 months)							
T2 assessment (6 months)							
T3 assessment (9 months)							
T4 assessment (12 months)							
T5 assessment (15 months)							

Figure 2. Flowchart of the study procedures

Table 1. Overview assessments								
Interviews:	Т0	МВСТ	T1	T2	Т3	T4	Т5	
SCID-1 (Full)	*							
SCID-1 (depression / mania)			*	*	*	*	*	
IDS-C	*		*	*	*	*	*	
YMRS	*		*	*	*	*	*	
FAST	*		*	*	*	*	*	
Self-report questionnaires:	Т0	МВСТ	T1	T2	Т3	T4	Т5	
СТQ	*							
TCQ	*							
STAI	*		*	*	*	*	*	
MHC-SF	*		*	*	*	*	*	
RRS-Br	*	*	*	*	*	*	*	
SCS-SF	*	*	*	*	*	*	*	
Q-IDS - SR		*						
ASRM		*						
CHIME	*	*	*	*	*	*	*	
RPA-NL	*	*	*	*	*	*	*	
EQ-5D-5L	*		*	*	*	*	*	
TiC-P	*		*	*	*	*	*	
Life CHART (incl medication	*							
Mfn adherence + Adverse events	*							
Cognitive measures:	то	МВСТ	T1	T2	Т3	T4	T5	

 
self-referent encoding task and trail making task (distraction)
 
breathing focus task
 
emotional stroop task
 
colour stroop task
 
Pavlovian instrumental transfer
 
Visual-analogue scale (mood rating; after breathing focus task)
 
	*		*					

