#### 7.2 AEs, SAEs and SUSARs

## 7.2.1 Adverse events (AEs)

Adverse events are defined as any undesirable experience occurring to a subject during the study, whether or not considered related to the mindfulness training. All adverse events reported spontaneously by the subject or observed by the investigator or his staff will be recorded.

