- Relapse into a (hypo)manic or depressive episode, which is an expected event in this specific population, since 60% of BD patients relapse within two years (Miklowitz et al., 2009; Oud et al., 2016). The study of Perich et al. (2013), who conducted a RCT of MBCT for BD, found that 59% of participants in the MBCT condition and 48% in the TAU condition reported a (hypo)manic episode, while 59% in the MBCT condition and 68% in TAU reported a depressive episode over a 12 month follow-up period. In that study, the median time to

(hypo)mania relapse was 130 days for MBCT and 143 for TAU. Median time to depressive relapse was 53 days for MBCT and 46 days for TAU.

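### As written, non-serious adverse events are prospectively elicited mainly in the MBCT arm, so a by-arm report of them would tend to look worse for MBCT

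*Protocol*

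**What the plan says.** Protocol section 6.3 describes the period after randomisation arm by arm, in three consecutive sentences.

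- MBCT arm: "Participants in the intervention group (MBCT + TAU) will receive an eight-week MBCT training, during which they daily have to document mood fluctuations" and other items in the Life Chart.
- Then: "Furthermore, participants are asked to document adherence and adverse events in a personal diary".
- TAU arm: "Participants in the comparator group (TAU) will receive their treatment as usual, while they daily document in the Life Chart as well".

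Table 1 in the same section has one row labelled "Mfn adherence + Adverse events", not split by arm.

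Section 7.2.1 defines an adverse event as "any undesirable experience occurring to a subject during the study, whether or not considered related to the mindfulness training", and has spontaneously reported and staff-observed events recorded. Section 7.2.2 adds an explicit question at each assessment, about unpleasant effects that seem to be caused by the MBCT training, and a check of the questionnaires by the principal investigators. In the event of adverse reactions, section 6.2 says that "patients are encouraged to discuss this with their MBCT teacher and responsible clinician".

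**The concern.** The definition in 7.2.1 applies to every subject and does not depend on a link to the training. The collection described in 6.3 and 7.2.2 does not match it. The diary appears only alongside the MBCT arm, and the one explicit question is framed around MBCT. The same non-serious event could then be written down in one arm and never reach the study in the other.

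Sections 7.4 and 9.3 call the risk negligible, and 7.4 dispenses with a DSMB on that ground. The trial's own adverse-event data are what would later support or challenge that judgement. With unequal elicitation, an apparent excess under MBCT could not be told apart from an effect of the diary, and a real excess could be explained away in the same manner. This is a fault of data collection: an analysis plan cannot recover TAU events that were never recorded.

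**Working it through.** The protocol states no adverse-event figure to reproduce, so the check is a comparison of the collection routes by arm.

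| Route | Protocol section | MBCT + TAU | TAU |
|---|---|---|---|
| Adverse-event diary | 6.3 | Described | Not mentioned |
| Daily Life Chart | 6.1.2, 6.3 | Kept; adverse events not listed | Kept; adverse events not listed |
| Question at each assessment | 7.2.2 | Fits the arm | Asks about a training not offered until after month 15 |
| Contact with an MBCT teacher | 6.2 | Yes | None |
| Spontaneous or staff-observed events | 7.2.1 | Yes | Yes |
| Questionnaire check | 7.2.2 | Yes | Yes |
| SCID-I, IDS-C, YMRS, FAST, STAI | Table 1 | Scheduled | Scheduled alike |

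**What TAU is given.** The TAU sentence carries over the Life Chart, not the diary. According to 6.3, patients "daily have to document mood fluctuations, changes in medication, and major life events in the Life Chart"; adverse events are not in that list.

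**Table 1.** Adverse events share a row with mindfulness adherence, which a TAU patient cannot have. That fits an MBCT-arm form. In the extracted table the row carries a single mark, as the Life Chart row does; a merged cell may have been lost, so it cannot settle duration.

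**Duration and form.** Section 6.1.2 runs the Life Chart over the whole 15 months. The paragraph on adherence measures in 6.1.3 puts mindfulness adherence on the Life Chart, while 6.3 puts adherence in a personal diary. The protocol therefore does not settle whether the diary is a separate form or how long it is kept.

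**Direction and possible size.** Let r be the true risk of a non-serious event, equal in both arms, and let d and c be the proportions captured in the MBCT and TAU arms. The observed risks are a = r·d and b = r·c. The observed ratio is a/b = d/c, whatever r is. Equal capture gives 1.0; d above c gives a ratio above 1.

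The protocol gives no value for r, d or c. All three are assumed below. The 80 per arm is the randomised number from section 4.4, before any loss to follow-up.

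Chance of a false significant excess under MBCT, two-sided 5% test, with p̄ = (a + b)/2:

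Φ{ [(a − b) − 1.96·√(2p̄(1 − p̄)/80)] / √[(a(1 − a) + b(1 − b))/80] }

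Example with r = 0.20, d = 0.90, c = 0.60: a = 0.18, b = 0.12, p̄ = 0.15. The numerator is 0.06 − 1.96 × 0.0565 = −0.0507 and the denominator is 0.0563, so the result is Φ(−0.90) = 18%.

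| Assumed true risk | d = 0.90, c = 0.60 (ratio 1.5) | d = 0.90, c = 0.30 (ratio 3.0) |
|---|---|---|
| 10% | 11% | 36% |
| 20% | 18% | 65% |
| 30% | 27% | 85% |
| 50% | 50% | 99% |

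With equal capture the chance in that direction is the nominal 2.5%. The table shows how sensitive a by-arm report would be to unequal capture. It does not estimate the bias in this trial.

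**The case against.** The best defence is that 6.3 never restricts the diary. It says participants, not participants in the intervention group, and the Table 1 row is not split by arm. Since 6.1.3 puts adherence on the Life Chart, the diary might even be part of the form that TAU also keeps. This stands in part: TAU is not explicitly excluded. But the order of the sentences and the pairing with mindfulness adherence both point to the MBCT arm, and a site following the text could leave the record out for TAU.

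Four stronger readings are tempting but not supported.

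- **All harm comparisons are biased.** No. Relapse, depressive and manic symptoms, anxiety and functioning are measured alike in both arms, and both keep the daily mood record.
- **TAU has nothing but spontaneous reports.** No. Staff-observed events, the questionnaire check and the assessment question also exist, although that question does little for a TAU patient.
- **The imbalance is confined to the eight-week course and can be sized from it.** The window is only inferred. The cited earlier trial does not help either: "Median time to depressive relapse was 53 days for MBCT and 46 days for TAU", but relapse is assessed here by SCID-I in both arms and says nothing about a diary imbalance.
- **A planned between-arm test will be wrong.** Section 8 states no adverse-event test, and its CONSORT sentence concerns clinical outcome data. Likewise, 6.2 encourages patients to talk to their teacher; it does not set up a formal reporting channel.

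**Conclusion.** The point holds in a limited form. As written, the protocol prospectively elicits non-serious adverse events mainly in the MBCT arm, against its own arm-neutral definition in 7.2.1. Any by-arm report of such events would tend to look worse for MBCT.

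This rests on two things: reading the diary sentence with the MBCT sentence before it, which is the more natural reading but not the only one, and assuming that a diary captures more events than the routes common to both arms. The direction follows from these. The size does not: the ratios of 1.5 and 3.0 and the false-signal chances of 11% to 99% come from assumed capture rates and risks. The efficacy endpoints and the relapse outcome are untouched. It is worth changing because the correction is cheap and the missing TAU data could not be recovered later.

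**What to change.** Reconcile section 6.3, the adherence paragraph in 6.1.3 and Table 1 so that they state:

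- that both arms keep the same adverse-event record, for the same stated period, for example as a line on the daily Life Chart, worded to match the definition in 7.2.1;
- that only the mindfulness-adherence record is specific to MBCT, with its own row in Table 1;
- that any between-arm summary of adverse events uses this common source, with events known only through MBCT teachers reported separately for that arm.

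The cost is a short text change and one added line on a form that TAU patients already complete daily. The downside is slightly more burden for TAU patients and more adverse-event processing in that arm.

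### Section 6.3 randomises after the T0 baseline but its Figure 2 randomises before it; a site following the figure could collect patient-reported baselines after the arm is known

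*Protocol*

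**What the plan says.** The text of protocol section 6.3 describes an intake visit with consent and eligibility screening: "They are thoroughly screened for in- and exclusion criteria with use of the SCID-I and YMRS". T0 follows, with the IDS-C and FAST interviews, optional computer tasks, and "self-report questionnaires at home (STAI, brooding subcale of RRS, CHIME, SCS-SF, MHC-SF, RPA, CTQ, TiC-P, and EQ-5D-5L". The text then says: "After baseline assessment, patients are randomised to one of two groups: TAU or MBCT + TAU".

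The same section states: "Figure 2 provides a flowchart of the study procedures from referral to the final assessment". In that figure the eligibility step ("Patient is invited for the research interview, in which the in- and exclusion criteria are assessed in detail") leads to a consent check, then to "Randomization (stratification variables: research centre; gender; depression status (current versus remitted); type of Bipolar Disorder; number of previous episodes", then to "T0 assessment (baseline", and only then to the two arms.

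On disclosure, section 6.2 says: "MBCT teachers on site will be notified of the allocation to MBCT, allowing them to invite the patient to participate". It keeps research assistants blind and says that nobody other than the assessors is. It does not link the notification of teachers, or the moment patients learn their arm, to completion of T0.

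**The concern.** Text and figure describe one sequence and put the same two steps in opposite order. In a multicentre trial where patients are not blinded, that order decides whether baseline answers can be influenced by knowing the allocation.

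Patient-reported scales are the most exposed. Someone who has just been assigned to, or passed over for, a sought-after training may rate anxiety, rumination or well-being differently. The TCQ, which asks about treatment credibility and expectancy, would partly reflect the allocation itself. The models in 8.1 and 8.2 use the baseline measurement, so a shift that differs between arms would enter the treatment comparison. In the economic evaluation, 8.2 also plans a baseline comparability check with adjustment if needed; there, a shift caused by disclosure could be treated as chance imbalance.

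**Working it through.** The check compares passages and counts measures. No figure in the plan depends on it.

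**1. Order of steps**

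| Source | Sequence |
|---|---|
| 6.3 text | intake (consent, SCID-I, YMRS) → T0 → randomisation → arms |
| Figure 2 | research interview and consent → randomisation → T0 → arms |

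Both put the eligibility interview before randomisation. They differ only on T0.

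**2. Does anything else settle the order?** The summary, section 3, section 6.2, section 8 and section 10.1 do not place randomisation relative to T0. Section 3 refers to Figure 1, whose content is not shown in the copy reviewed. The drawing of Figure 2 is not shown either, only its extracted text. Its other boxes, from recruitment to T5, come out in logical order, so a swap of this one pair in extraction is unlikely.

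**3. What protects T0 under each order?**

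- 6.3 text: an arm that has not been generated cannot be disclosed, so the order itself protects T0. One gap remains. The questionnaires are completed at home, and the text does not say they must be returned before randomisation.
- Figure 2: the allocation exists before T0. Section 6.2 gives no rule that holds it back from teachers or patients until T0 is complete.

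**4. Which measures are exposed?**

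- Home list in 6.3: STAI, RRS brooding, CHIME, SCS-SF, MHC-SF, RPA, CTQ, TiC-P, EQ-5D-5L = 9.
- Table 1 adds the TCQ at T0: 9 + 1 = 10 self-report questionnaires.
- Secondary scales in 8.2: YMRS, FAST, STAI, RPA, MHC-SF, SCS-SF, CHIME, RRS brooding = 8. Of these, 6 are on the home list (6/8 = 75%); YMRS and FAST are clinician-rated.
- The EQ-5D-5L, used for the cost-utility analysis, is also on the home list.
- The CTQ (childhood events) and TiC-P (resource use) are on the list too, but are less obvious candidates for a shift.

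**5. Primary endpoint.** This is the IDS-C at T1, rated by blinded assessors. The baseline IDS-C enters the repeated-measures model in 8.1 and rests on patients' answers, so it is not immune, but it is less exposed than a home questionnaire. A T1 comparison that did not use baseline would be unaffected.

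**The case against.** The best defence is that the 6.3 text is explicit and sound: it describes T0, home questionnaires included, and then randomises. On that reading Figure 2 is a drafting slip. Even Figure 2 splits the arms only below the T0 box, which fits an allocation generated early and acted on after baseline. Harm needs a site to follow the figure rather than the text, and patients to be told before they finish T0. Nothing shows that this would happen.

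Most of this stands, and it limits the point. A reader might infer that the protocol has no safeguard and that baselines will be collected unblinded. The documents do not support that, because the text order, if followed, is a safeguard. A reader might also infer that allocation concealment or patient selection is compromised. That is not supported either, since eligibility is assessed before randomisation in both versions. Nor is there support for calling the primary result biased, given blinded rating of the IDS-C at T1.

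The defence does not remove the contradiction. Sites hold both descriptions, no sentence says which governs, and none says that an allocation made before T0 is withheld. The home forms are left open even under the text order. The TCQ is missing from the 6.3 list and appears only in Table 1, so its timing relative to allocation depends entirely on where T0 falls.

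**Conclusion.** The contradiction between the 6.3 text and Figure 2 is real, subject to the figure having been read from extracted text and Figure 1 being unavailable. The consequence is conditional. If Figure 2 is followed and the arm is disclosed before T0 is complete, baselines for 6 of the 8 secondary scales, the EQ-5D-5L and the TCQ could come from patients who know their arm. If the 6.3 text is followed, only home questionnaires returned after randomisation are exposed.

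The size and direction of any shift cannot be estimated from the protocol. The sample size is not affected. Confidence is high that text and figure disagree, and low to moderate that baselines would in practice be collected after disclosure. It should be fixed because the correction is simple and a baseline collected after disclosure cannot be recovered.

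**What to change.** Redraw Figure 2 with the T0 box above the randomisation box, to match the 6.3 text, and check that Figure 1 shows the same order. Add one sentence to 6.2 or 6.3: randomisation, and disclosure of the result to teachers and patients, take place only after the T0 measures, including the home questionnaires and the TCQ, have been completed or declined.

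The cost is one redrawn figure, one sentence, and possibly a short wait for home forms before allocation; the protocol gives no figure for how long that would be. The number of patients, the visits and the measures do not change.
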